5. OBJECTIVES

5.1 *General Objective*

To evaluate differences in the response of weight, body composition and metabolic biochemical parameters among obese patients following a normoprotein low-fat controlled ketogenic diet compared to a balanced BIEM).

5.2 *Specific Objectives*

- Intra- and intergroup comparison of patient weight and BMI reduction between baseline and subsequent follow-up monitoring visits.
- To determine the percentage of patients with weight loss equal to or greater than 10% of initial weight and the time it took for patients to reach this figure.
- Evaluate the evolution of comorbidities associated with obesity (HT, hyperglycemia or diabetes, hypercholesterolemia, hypertriglyceridemia, apneas), control of clinical and analytical parameters and changes in medication during the weight loss process and during follow-up.
- To know the tolerability of the diet: Incidence of side effects during the development of the study,
- Safety of the intervention diet: appearance of analytical alterations, especially of the ionic profile, renal function and hepatic function, incidence of serious adverse events.
- Assess diet adherence and dropout rate and cause.
- To know patient satisfaction with the assigned nutritional program.

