6. HYPOTHESIS

Assumption 1: **Weight Loss** .

H1: The use of the "Zélé method" (**Tx1**) allows a greater weight loss (*pp*) than a hypocaloric diet (**Tx2**) in the same time (*t*).

Assumption 2.

H2: Tx1 is safe and with low or no adverse effects.

Assumption 3. **Metabolic conditions**

H3: *pp* with Tx1 allows the regulation of metabolic syndrome and its components.

H4: The state of controlled ketosis that occurs with Tx1 does not change pH or raise blood lactate levels.

Assumption 4 . **Body Composition**.

H5. Tx1 will produce a selective loss of fat and preservation of muscle mass.

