7. METHODOLOGY

7.1. Study setting.

The study will be conducted in Mexico City under the sponsorship of Zélé® and in collaboration with the VIME Weight Loss and Wellness Center of Mexico. During the year 2021 and with follow-up for 24 months. An open call will be made through different media including social networks for the recruitment of patients who meet the inclusion criteria and must present themselves for a clinical evaluation in which pathological history, clinical status, heart rate, blood pressure, oxygenation and temperature will be recorded. Nutritional assessment in which anthropometry and multifrequency electrical bioimpedance analysis (MFBIA) will be performed to determine body composition. Patients will have to bring a Complete Blood Count, a biochemical profile that includes the following determinations: Fasting blood glucose, glycosylated hemoglobin, urea, creatinine and uric acid, cholesterol, triglycerides, LDL, HDL and VLDL, direct and indirect bilirubins, alanine and aspartate aminotransferases, gamma-glutamyl transferase and albumin, determination of serum electrolytes sodium, chloride, potassium, magnesium, phosphorus and calcium, Fasting Insulin , HOMA index calculation. In addition to a thyroid function panel and arterial blood gases. They will be instructed during recruitment for the studies to be performed in a clinical laboratory, under the current standardization and with standardized and perfectly calibrated automated equipment, and a request will be made to keep the vials of the patients' plasmas. Patients who meet all the inclusion criteria will be selected and will have an interview with the principal investigator in which they will sign their letter of commitment and informed consent, then they will be subjected to the randomization process with a 2:1 allocation for treatment and controls, respectively. Subsequently, they will be submitted to the two nutritional treatments and will be clinically evaluated every week and will receive nutritional, psycho emotional and physical activity counseling. At each visit, adverse effects, changes in clinical status will be recorded and the presence of ketone bodies in capillary blood will be determined with the Freestyle Abbott optium H β -Ketone (β -hydroxy-Butyric Acid) device; during nutritional counseling, MFBIA will be performed using the In-Body 570 body composition analyzer. When ketone body levels above 0.8 mmol/liter are detected, a new arterial blood gas analysis will be taken; for patients who do not have elevated ketone bodies, an arterial blood gas will be taken between the first and second week of treatment. A new biochemical profile determination will be performed when patients have lost 40% of their overweight or between 10 and 12 kg, whichever

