
occurs first. And new biochemical evaluations when the decrease of Ketone Bodies below 0.4 mmol/l is detected or when patients have reached a loss of 60 to 70% of their overweight and one more when they reach their weight loss goal. Subsequently, only clinical and nutritional follow-up will be given along with psycho-emotional support and physical activity advice every 3 months up to 12 months and every 6 months up to 24 months.

7.2 Study design.

Longitudinal, Prospective, Controlled Randomized Clinical Trial.

7.3 Study population.

Patients of either sex, between 18 and 60 years of age, with a body mass index (BMI) between 30 and 35 kg/m².

7.4 Sample.

The sample will be obtained by open call through social media and all patients who come with their clinical analysis and meet the inclusion criteria will be evaluated until the sample number is reached. In order to obtain 95% power in this Controlled Clinical Trial and with a 95% CI, a 3:1 case-control ratio is established, considering a 35% attrition rate, 56 cases and 32 controls will be included and subsequently crossed to become cases. (Calculated with EPIinfo STATCALC for sample size)

Two blinded arms are proposed for the physician and the patient.

Obese patients assigned to the low-fat normoprotein controlled ketogenic diet group.

Obese patients assigned to a balanced hypocaloric diet. And who will subsequently be subjected to a controlled normoproteic low-fat ketogenic diet.

7.5 Inclusion, exclusion and elimination criteria.

7.5.1 Inclusion:

- Men and Women
- 18 to 60 years of age
- With BMI between 30 and 35 Kg/m²
- Who has not taken weight loss treatment in the last 6 months

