Arterial pH	Indicates the amount of hydrogen ions contained in the blood.	Determines the degree of acidity or alkalinity of the blood.	Quantitative, Ratio minimum 7.35 maximum 7.45	Registration form. Blood analysis
Lactic Acid	Substance produced by muscle tissue and blood cells. Lactic acid levels increase when oxygen levels decrease.	Acidic substance that accumulates in the blood and causes a decrease in pH, its ionized form is lactate.	Quantitative, Ratio 4.5 to 19 mg/l or 0.5 to 2.2 mmol/liter.	Registration form. Blood analysis
Anion Gap	Difference between anions and cations measured in the serum	Difference between anions and cations measured in serum	Quantitative, Ratio unit mEq/l minimum 8 max. 12	Registration form. Blood analysis
Excess Base	the amount of acid required to return the pH of an individual's blood to a normal value	the amount of acid required to return the pH of an individual's blood to a normal value	Quantitative, Ratio Minimum -2 maximum + 2	Registration form. Blood analysis

Satisfaction and Adherence				
Satisfaction Survey	Positive assessment of the different dimensions of the medical care received	Interrogation Very Satisfied to Very Dissatisfied	Categorical Nominal	Registration form.
Adherence to treatment	Taking medication according to the dosage of the prescribed schedule; and persistence, taking medication over time.	Interrogation Complied or did not comply with the program.	Categorical Nominal	Registration form. adherence to treatment

7.7 Data collection.

All data will be captured and recorded digitally in each of the queries through the Google Forms platform to consolidate the information in Google Sheets.

In the consultation, medical history data will be collected in the form of interrogation, weight will be determined through electronic scales, height through calibrated stadiometers, All measurements will be performed according to the WHO Physical Measurement Guide 2014 (www.who.int/surveillance/steps/Part3_Section4) Annex 1. In addition, a capillary determination of glucose and ketones will be performed at each clinical consultation. Once patients are drawn by lot they will be assigned to one of the control centers distributed in Mexico City, they will always have to go to the same control center (VIME). The consultation visits will be weekly for weight control and clinical check-up and every two weeks alternately for physical and psychological counseling.

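### In the visible schedule, venous glucose and HbA1c after baseline are taken only at weight-loss, ketone-fall or goal-weight events, so comparing arms at those profiles does not estimate the effect of assignment

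*Combined protocol and SAP*

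**What the plan says.** The general objective (5.1) is to evaluate "differences in the response of weight, body composition and metabolic biochemical parameters among obese patients" on the two diets. Section 7.9 plans tests within and between groups and names no time point.

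The baseline profile in 7.1 includes fasting glucose and HbA1c. The later profiles in 7.1 are these:

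- First, on weight: "A new biochemical profile determination will be performed when patients have lost 40% of their overweight or between 10 and 12 kg". The earlier of the two applies.
- Next, on ketones: "new biochemical evaluations when the decrease of Ketone Bodies below 0.4 mmol/l is detected". A weight trigger is the alternative here, at 60-70% of overweight.
- Last: a profile at goal weight.

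After goal weight, 7.1 provides clinical and nutritional follow-up only, every three months to month 12 and every six months to month 24.

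For arterial blood gas, 7.1 does give a calendar fallback: "for patients who do not have elevated ketone bodies, an arterial blood gas will be taken between the first and second week of treatment".

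Section 7.7 adds that "a capillary determination of glucose and ketones will be performed at each clinical consultation" and that "The consultation visits will be weekly for weight control and clinical check-up". Blood ketones have a row in 7.6; capillary glucose has none.

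**The concern.** The triggers depend on weight loss, which is what the diets are meant to change. Three things follow for a between-arm comparison at triggered profiles.

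- **Who is measured.** A patient who meets no trigger may have no venous value after baseline. If H1 is true, more of these patients are controls.
- **When.** The faster arm is sampled earlier.
- **At what weight loss.** At a weight trigger, both arms have lost about the same share of overweight, or about the same kilograms. Any glycaemic benefit that comes from losing more weight largely drops out.

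The ketone trigger does not repair this. A control who never enters ketosis has no fall to detect. In the ketogenic arm a fall can mean planned exit from ketosis or non-adherence, so some low responders are sampled there but not among controls.

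At stake is the glycaemic part of the general objective. Weight loss (H1) is not affected.

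**Working it through.** The plan gives no figure for this comparison. Its sample size cannot be reproduced, because no effect size or SD is stated, and the point does not depend on it.

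**1. Timing rules after baseline, visible text**

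| Measurement | Rule | Calendar timing? |
|---|---|---|
| Venous glucose, HbA1c (7.1) | Weight loss, ketone fall or goal weight | None |
| Arterial blood gas (7.1) | Ketones above 0.8 mmol/l | Yes, week 1-2 |
| Capillary glucose (7.7) | Each clinical consultation | Yes, weekly |

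**2. Where the first weight trigger lies.** The protocol does not define overweight in kilograms. I take weight above BMI 25, where 7.6 starts the overweight band. The trigger as a share of body weight is 0.4 × (1 − 25/BMI).

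- BMI 30: 0.4 × (1 − 25/30) = 6.7%.
- BMI 32.5: 0.4 × (1 − 25/32.5) = 9.2%.
- BMI 35: 0.4 × (1 − 25/35) = 11.4%, or less where the 10-12 kg rule comes first.

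At BMI 32.5 and an assumed height of 1.65 m, this is 0.4 × 7.5 × 1.65² = 8.2 kg.

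**3. When it is reached.** Week = 8.2 kg ÷ weekly loss. At assumed losses of 1.5, 1.0, 0.5 and 0.3 kg/week, the trigger falls at weeks 5.4, 8.2, 16.3 and 27.2.

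**4. Effect on the comparison (illustration).** Trials of 56 and 32 patients were simulated 4,000 times. Assumptions: BMI uniform over 30-35; mean height 1.65 m (SD 0.08); trigger at the lesser of 40% of overweight and 10 kg; coefficient of variation of weekly loss 35%; glucose falls 1 mg/dl per kg lost; noise SD 8 mg/dl; no dropout. The triggered comparison uses patients who reach the first trigger by week 12.

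| Loss, kg/week (ketogenic, control) | Triggered by week 12 | Median trigger week | Difference at matched week 12, mg/dl | Difference at first triggered profile, mg/dl |
|---|---|---|---|---|
| 1.5, 0.5 | 94%, 22% | 5.4, 16.2 | −12.0 | −1.2 |
| 1.2, 0.6 | 89%, 39% | 6.7, 13.5 | −7.1 | −0.6 |
| 1.0, 0.7 | 81%, 54% | 8.1, 11.6 | −3.6 | −0.3 |
| 0.8, 0.8 | 66%, 66% | 10.1, 10.1 | 0 | 0 |

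Simulation error is about 0.1 mg/dl. The week-12 differences agree with 12 × the gap in weekly loss (12 × 1.0 = 12.0 in the first row). The near-disappearance at the trigger follows from letting glucose change only through weight. A direct effect of ketosis on glucose would survive. With equal loss rates there is no distortion.

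**5. The ketone trigger.** Controls at 1,200-1,400 kcal with 50% carbohydrate (7.10.2) take 1,200 × 0.5/4 = 150 g to 1,400 × 0.5/4 = 175 g per day. Frank ketosis allows less than 60 g (7.10.1).

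**6. Precision.** With 35% attrition (7.4), 56 × 0.65 = 36.4 and 32 × 0.65 = 20.8, so about 36 and 21 remain. The 95% CI half-width in SD units is t × √(1/n₁ + 1/n₀).

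- All at one matched week: 2.00 × √(1/36 + 1/21) = 0.55 SD.
- If 80-100% of the ketogenic arm and 25-75% of controls trigger (assumed), 29-36 and 5-16 remain. The half-width is then 0.60 SD (36 and 16) to 0.99 SD (29 and 5).

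**7. Why no bias is quoted in SD.** Patients are sampled when they cross the threshold. Assume normality, correlation r between weight loss and glucose fall, and share p triggered. Relative to all controls at a common time, triggered controls then differ by r × z(1 − p), positive meaning that they look better. With r = 0.3-0.5 this is +0.20 to +0.34 at p = 25%, zero at 50%, and −0.20 to −0.34 at 75%. Net of the same term in a ketogenic arm with 80-90% triggered, it runs in favour of controls from 0.3 × (−0.674 + 0.842) = 0.05 to 0.5 × (0.674 + 1.282) = 0.98 SD. None of these inputs is in the documents, and the range is too wide to use.

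**The case against.** **H3 has no comparator.** It says that weight loss "with Tx1 allows the regulation of metabolic syndrome and its components", and only H1 sets equal time. Sampling at weight-loss milestones suits a within-arm reading of H3. This stands: a reader might infer that H3 cannot be examined, and the documents do not support that. But the general objective is comparative, and 7.9 plans between-group tests.

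**A contrast at equal weight loss is a legitimate question.** It asks what the diet does beyond weight loss. That is true, but it is a different question. The plan does not say that it wants it, and the missing low responders and unequal weeks would remain.

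**The text is incomplete.** The timeline in section 10 is not shown, and the venous-sample sentence in 7.7 breaks off at glycosylated haemoglobin. A reader might infer that no fixed-week sample exists anywhere. The documents support only that none is visible. If the timeline sets one, the point falls for that sample.

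**Weekly capillary glucose is also selected.** A reader might infer that matched weeks are free of selection on response. The plan contradicts this. Section 7.5.3 removes patients whose diabetes control worsens, which is withdrawal on glycaemia itself. Patients at goal weight leave weekly visits. Controls cross over at an unstated time. This stands in full and limits the remedy.

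**The remedy is partial and not wholly in hand.** Section 7.1 lists only ketones among capillary readings at each visit, and no fasting state is set for capillary glucose. Lipids, renal, hepatic and electrolyte results share the same trigger timing and are not helped. This also stands.

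**Conclusion.** The concern holds for the visible text. Whenever the arms lose weight at different rates, a between-arm test of venous glucose or HbA1c at triggered profiles compares differently selected patients, at different weeks and at similar weight loss. It does not estimate the effect of assignment.

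The direction of the distortion follows from the design, but its size does not. It depends on trigger rates, loss rates and the link between weight and glucose, none of which the documents give. The table shows roughly a tenfold shrinkage of the difference under assumptions that put the whole effect through weight. It is an illustration, not a forecast, and a single bias figure in SD units would not be supported.

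Glycaemia is one of several biochemical and comorbidity outcomes and H1 is unaffected, so this is a minor to moderate point to consider. Confidence is medium because the timeline is not visible.

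**What to change.** 1. **7.9:** label venous glucose and HbA1c comparisons at triggered profiles as descriptive. Give the number contributing and the week of sampling by arm.
2. **7.1, 7.6, 7.7:** confirm that capillary glucose is recorded at each weekly visit, add it to 7.6 beside blood ketones, record fasting status, and take a reading before the diet starts.
3. **7.9:** compare arms on capillary glucose at matched weeks, within the weekly-visit period and before controls cross over (state when that is). Use a repeated-measures mixed model adjusted for the pre-diet reading.
4. **Reporting:** describe this comparison as not conditioned on reaching a weight-loss trigger. Report by arm the withdrawals for worsening diabetes control and the patients who left weekly visits after reaching goal weight.

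The cost is protocol wording, a form field for fasting status and one more analysis. Capillary readings are less precise, may not be fasting, and do not replace HbA1c or the other triggered biochemistry. The fuller remedy is a set-week venous profile for patients who have met no trigger, modelled on the blood-gas fallback in 7.1. It would give such patients a later venous value, at added laboratory cost.

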Blood samples will be collected in Specialized Clinical Laboratories according to NOM-253-SSA1-2012 and the laboratory sample collection manual in force in each laboratory. A venous sample will be taken to determine Complete Blood Biometry, Blood Chemistry of 27 elements, Basic thyroid profile, Glycosylated

7.8 Measuring instruments.

With all the data, a database will be built in Excel MS®. Patient satisfaction will be measured with the Likert Scale, which consists of 5 possible answers per item: very satisfied, satisfied, indifferent, dissatisfied and very dissatisfied. (attached)

7.9 Statistical analysis.

Descriptive statistical tests will be performed establishing general and group measures, determining variability measures such as standard deviation and Confidence Interval, comparative inferential tests will be performed within and between groups, for quantitative variables it is proposed as an initial T-test, which will be contrasted according to the conditions of normality and homoscedasticity of the sample. For qualitative variables, χ^2 is initially proposed, which will be contrasted according to the same conditions; one-way ANOVA and repeated measures ANOVA will also be used. Microsoft Excel 365 and SPSS V 21

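### Section 7.9 plans within-group tests but names only chi-square for qualitative variables, which is invalid for before/after status in the same patients

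*Combined protocol and SAP*

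**What the plan says.** Section 7.9 commits to testing in both directions: "comparative inferential tests will be performed within and between groups". It then chooses tests by type of variable. Quantitative variables get a t-test, "which will be contrasted according to the conditions of normality and homoscedasticity of the sample". The rule for the rest is: "For qualitative variables, χ^2 is initially proposed, which will be contrasted according to the same conditions". It adds that "one-way ANOVA and repeated measures ANOVA will also be used", without tying either method to a variable. No McNemar, Cochran Q, marginal-homogeneity or GEE analysis is named.

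Three other places bear on the point:

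- Section 5.2 sets the objective "Evaluate the evolution of comorbidities associated with obesity (HT, hyperglycemia or diabetes, hypercholesterolemia, hypertriglyceridemia, apneas" and also covers changes in medication. It assigns no test and no pair of visits.
- Section 6 states H3 as weight loss that "with Tx1 allows the regulation of metabolic syndrome and its components". It names no comparator, endpoint or test.
- Section 7.6 lists HbA1c as ordinal in five levels and fasting glucose by cut-off classes. Blood pressure, triglycerides and HDL are listed as quantitative, and waist in centimetres. There is no variable for metabolic-syndrome status, apnoea or medication.

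**The concern.** A categorical result recorded at two visits in one patient is a matched pair. Chi-square for two proportions assumes independent observations. A statistician who follows 7.9 literally has within-group comparisons to make, qualitative variables to make them on, and one named test. The stated grounds for leaving that test concern the distribution of quantitative data. They say nothing about pairing, so they can never lead to a paired method. Repeated measures ANOVA is a method for quantitative outcomes and does not fill the gap for binary or ordinal status.

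Such comparisons are likely. The comorbidity objective is about change over time, and H3 is worded for one treatment alone. Section 7.4 also has the controls cross to the ketogenic diet. After that no concurrent control remains, and later change can be judged only within patients. At stake is what the trial reports on comorbidity: a real fall in prevalence could be missed, or a small p-value could be read as change when it shows only that baseline status predicts later status.

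**Working it through.** The plan gives no figure for this analysis, so there is nothing to reproduce.

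**Inputs from the documents.** Section 7.4: 56 patients on the ketogenic diet and 35% attrition, hence 56 × 0.65 = 36.4, or about 36 completers; 95% confidence, taken as two-sided α = 0.05.

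**Assumed inputs.** Prevalence 50% at both visits (no change) or falling from 50% to 30%; within-patient correlation ρ from 0 to 0.6.

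**Step 1: why independence matters.** For prevalences p₁ and p₂ in the same n patients, the variance of the difference is [p₁q₁ + p₂q₂ − 2ρ√(p₁q₁p₂q₂)]/n. Chi-square on 2n rows uses 2pq/n with pooled p. With no change, the true variance is (1 − ρ) times the assumed one. The real type I error is therefore about P(|Z| > 1.96/√(1 − ρ)):

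- ρ = 0.3: cut-off 2.34, error 1.9%
- ρ = 0.5: cut-off 2.77, error 0.6%
- ρ = 0.6: cut-off 3.10, error 0.2%

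**Step 2: simulation of paired binary data.** Percentage of trials rejecting:

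| n, change | ρ | Chi-square, 2n rows | McNemar | Exact McNemar | Before-by-after table |
|---|---|---|---|---|---|
| 56, none | 0 | 4.7 | 5.3 | 3.0 | 4.9 |
| 56, none | 0.3 | 1.8 | 5.2 | 3.0 | 61.4 |
| 56, none | 0.5 | 0.5 | 4.6 | 2.6 | 97.5 |
| 36, none | 0.5 | 0.5 | 4.4 | 2.1 | 88.7 |
| 56, 50% to 30% | 0 | 57.8 | 58.9 | 49.4 | 5.1 |
| 56, 50% to 30% | 0.5 | 60.5 | 87.3 | 81.6 | 98.3 |
| 36, 50% to 30% | 0.5 | 36.7 | 67.5 | 56.0 | 89.9 |

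The simulated errors agree with step 1. The last column responds to ρ and hardly at all to whether prevalence changed: at ρ = 0.5 and n = 56 it rejects in 97.5% of trials with no change and 98.3% with a 20-point fall.

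**Step 3: one data set, three answers.** Take 36 patients: 10 affected at both visits, 8 resolved, 1 new, 17 never affected. That is 18 affected before and 11 after.

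- Chi-square on 72 rows: pooled p = 29/72 = 0.403; χ² = (7/36)² / (0.403 × 0.597 × 2/36) = 2.83, p = 0.093.
- McNemar: (8 − 1)²/(8 + 1) = 5.44, p = 0.020; exact p = 2 × P(X ≤ 1 | 9, ½) = 20/512 = 0.039.
- Before-by-after table: 36 × (10 × 17 − 8 × 1)² / (18 × 18 × 11 × 25) = 10.60, p = 0.001. This answers a different question.

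**The case against.** The plan nowhere says that chi-square will be applied to before/after comorbidity status. It calls the test initial, and it says t-test without paired or unpaired, so both may be meant as names of test families. The one objective that states an intragroup comparison concerns weight and BMI, both quantitative. The variables labelled nominal in 7.6 are sex, satisfaction and adherence, none of them a before/after comorbidity. This stands. The use of chi-square on paired status follows from reading two general sentences together; it is not an express assignment.

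A reader might infer that H3 as a whole will be tested wrongly. The documents do not support that. H3 has no assigned test, and blood pressure, triglycerides, HDL and waist are recorded as measured values, which belong to the t-test or repeated measures ANOVA.

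The numbers are also less one-sided than they can be made to look. Exact McNemar is itself conservative: 2.1% to 3.0% in the no-change rows above. At zero correlation the independent-rows test loses almost nothing and is more powerful than exact McNemar. The before-by-after table then rejects in only about 5% of trials. If chi-square were run on independent rows with positively correlated status, the error would cost power and would not create a false claim of benefit. Finally, a correct paired test within one arm is still not a randomised comparison.

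The core survives. Within-group tests are planned, no paired categorical method is named, and the stated conditions for changing the test cannot supply one.

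**Conclusion.** The gap is real and of moderate severity. Applied as written to repeated categorical status in the same patients, 7.9 leads to an invalid test. Treated as independent samples, the comparison is conservative and loses power under positive within-patient correlation. Cross-tabulated, it does not test change at all.

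The reach is limited to the comorbidity objective where status is coded in classes, to HbA1c and glucose classes, and to H3 only as far as its components are categorised. H1 (weight) and H5 (body composition) rest on quantitative variables and are unaffected, as are categorical comparisons between the arms. The sample size statement is a separate matter.

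All power and error figures above rest on assumed prevalences and correlations. The invalidity under pairing does not depend on them, but its size and direction do.

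**What to change.** Amend 7.9 so that qualitative comparisons within a group have their own rule:

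- **Binary status at two visits:** McNemar's test with a paired confidence interval for the change in prevalence. State whether the exact or asymptotic form is used, since they differ at this sample size.
- **Ordered classes, such as HbA1c as now defined:** a paired ordinal or marginal-homogeneity test, or analysis of HbA1c as a continuous value. McNemar's test does not fit five levels.
- **More than two visits:** logistic GEE with the patient as cluster.
- **Between the randomised arms:** keep chi-square.

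In the same edit, name the endpoint, visits and test for H3, and say which comorbidities will be analysed as present or absent. Remove normality and homoscedasticity as the conditions for changing the chi-square test.

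The cost is a few sentences. For variables already recorded no new data are needed, because McNemar's test and the paired interval use only the four cell counts. Apnoea and medication have no entry in 7.6 and would need one.
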